14.1. Multicenter Publication

The sponsor may invite the investigator to participate in a multicenter publication of the study results, in which case it will be ensured that the documents submitted for publication comply with the publisher's requirements for authors and contributors. If the publisher has no such requirements, it will be ensured that the publication meets the authorship and contributorship requirements as stated in the current Smith & Nephew Global Policy and Procedure relating Scientific Disclosures. Also, the sponsor will select a publisher based on mutual agreement with the investigators, who are invited to participate in the publication.

Investigator Publication

The investigator may publish his/her own data subject to the following restrictions:

- the multicenter manuscript must be published prior to investigators publishing their own data;
- the manuscript shall be submitted to the Sponsor for review prior to submitting the manuscript for publication;
- the manuscript must reference the study multicenter manuscript.

15. Authorship

The sponsor may invite the investigator to participate in a multicenter publication of the study results. The sponsor will select a publisher based on mutual agreement with the investigators who are invited to participate in the publication. Unless otherwise required by the journal of publication or the forum in which a presentation is made, authorship will comply with International Committee of Medical Journal Editors (ICMJE) current Uniform Requirements for Manuscripts Submitted to Biomedical Journals: Writing and Editing for Biomedical Publication. ICMJE recommends that authorship be based on the following criteria:

- Substantial contributions to the conception or design of the work; or the acquisition, analysis, or interpretation of data for the work; and
- Drafting the work or revising it critically for important intellectual content; and
- Final approval of the version to be published; and
- Agreement to be accountable for all aspects of the work in ensuring that questions related to the accuracy or integrity of any part of the work are appropriately investigated and resolved.
- In addition to being accountable for the parts of the work he or she has done, an author should be able to identify which co-authors are responsible for specific other parts of the work. In addition, authors should have confidence in the integrity of the contributions of their co-authors.

Subject to a publisher's copyright, Site and/or Investigator will own the copyright on publications and other copyrightable material produced as a result of the Study.

16. Protocol Amendments

It will be necessary to obtain FDA and EC / IRB approval prior to implementation of any change in the protocol that may affect the scientific soundness or the rights, safety, or welfare of the subjects involved. Notification shall be submitted to the EC / IRB of the study site by the Investigator.

17. Risk - Benefit Analysis

A. Study Related Risks

Possible risks that may occur as a result of long term follow-up study participation are:

- Subjects will be asked to return to their doctor for follow-up visits at 5, 7 and 10 years and undergo an evaluation to assess their pain and function; however, these are not interventional procedures and are not expected to add significant time to any appointments.
- This study involves the use of x-ray evaluation. X-ray exposure is cumulative over a lifetime and total exposure should be kept to a minimum. However, if the x-ray exposure when participating in the study is equivalent to the exposure the subject would receive if they chose not to participate in the study, there is no additional risk associated with this study.
- As a result of participating in the study there could be a risk of loss of protected subject information confidentiality.
 All applicable confidentiality standards and data protection and privacy laws will be followed by the Sponsor to ensure that data collected is handled in confidence. Data will be coded and handled only by appropriately qualified and authorized personnel.

B. Study Related Benefits

Because the surgery and all the follow-up visits are the same as when the subject would not participate in this study, there are no additional medical benefits associated by participating in this study. The information gained from this study may help improve the treatment of people that need to undergo total hip replacement.

18. Applicable norms and guidelines

Clinical Investigation: ISO 14155:1 and ISO 14155:2

Reporting: STROBE: Strengthening the Reporting of Observational Studies in Epidemiology)

References

- 1. Canadian Institute for Health Information. 2005.

	ADDENDUM Page: 5 of 25

ABBREVIATIONS & DEFINITIONS

AE	Adverse Event
ADE	Adverse Device Effect
AP	Anteroposterior
CAPA	Corrective and Preventive Action
CoC	Ceramic-on-ceramic
СоР	Ceramic-on-polyethylene
CRO	Contract Research Organization
CRF	Case Report Form
DOD	Biolox delta ceramic on ceramic
EC	Ethics Committee
EU	European Union
FDA	Food and Drug Administration
FU	Follow-Up
GCP	Good Clinical Practice
HHS	Harris Hip Score
ICF	Informed Consent Form
ICH	International Conference on Harmonization of Technical Requirements for Registration of Pharmaceuticals for Human Use
IRB	Institutional Review Board
МоР	Metal-on-polyethylene
PI	Principal Investigator
SAE	Serious Adverse Event
SADE	Serious Adverse Device Effect
THA	Total Hip Arthroplasty
THP	Total Hip Prosthesis
USADE	Unanticipated Serious Adverse Device Effect
XLPE	Cross Linked Polyethylene

Post-Approval Study of the R3 Biolox delta Ceramic Acetabular System – Europe	Protocol Number: R3H01/02/01/2017/Version2.0
	PMA Number P150030
	ADDENDUM Page: 6 of 25

Protocol Synopsis:

Title of Study:	Post-Approval Study of the R3 Biolox Delta Ceramic Acetabular System – Europe	
Study Type:	Post-market Outcomes Study	
Study Device:	R3 delta Ceramic Acetabular System	
Indications	The R3 Ceramic Acetabular System is indicated for use in skeletally mature patients requiring primary total hip arthroplasty due to non-inflammatory arthritis (degenerative joint disease) such as osteoarthritis, avascular necrosis, or traumatic arthritis.	
Study design: Prospective, multicenter, observational study		
Primary Endpoint: The primary endpoint is implant survivorship at 10 years post procedure.		
Secondary Endpoints:	Secondary endpoints include patient satisfaction measured by clinical assessment of pain and function and a radiographic evaluation.	
Length of Study:	Subjects will be followed to the 10-year postoperative interval.	
Number of Sites:	Five (5) sites	
Sample Size:	135 subjects	
Inclusion Criteria:	Subjects who met all inclusion criteria and none of the exclusion criteria for inclusion of their records in the PMA Cohort presented in the R3 Biolox delta Ceramic Acetabular System PMA clinical report (Subjects in the DOD treatment arm of the PMA Cohort) will be included in this PAS.	
Exclusion Criteria:	Subjects in any of the other treatment arms of the original European Post-market Study are excluded from this PAS.	

Post-Approval Study of the R3 Biolox delta Ceramic Acetabular System – Europe	Protocol Number: R3H01/02/01/2017/Version2.0
	PMA Number P150030
	ADDENDUM Page: 7 of 25

BACKGROUND AND STUDY RATIONALE

1.1. Background

Smith & Nephew Orthopaedics is the sponsor of a prospective, multicenter, non-randomized, clinical outcomes study of the R3 delta Ceramic Acetabular System in patients with degenerative hip disease in Europe. The study was designed to evaluate the performance of the R3 cup with multiple articulation couples including the Biolox delta ceramic-on-ceramic (DOD) and the Oxidized Zirconium-on-crosslinked polyethylene (OxZr/XLPE) articulation couple. The study devices were commercially available in Europe at that time, and the study satisfied EU post-market surveillance requirements. The study was conducted in compliance with ISO 14155 and International Conference on Harmonization Good Clinical Practice (ICH GCP) Guidelines (Notes for Guidance on GCP CPMP/ICH/135/95); National Statement on Ethical Conduct in Research Involving Humans, consisting of a series of Guidelines made in accordance with the National Health and Medical Research Council Act 1992; World Medical Association Declaration Of Helsinki - Ethical Principles for Medical Research Involving Human Subjects October 2008; and 21 CFR 812 revised April 1st, 2008 (Medical Devices), as well as with all applicable local laws and regulations.

Clinical data from this study was used to support a Premarket Approval Application (PMA) that was submitted to the US FDA in August 20, 2015. In the PMA, only data on DOD and OxZr/XLPE subjects were included. Approval was sought for the DOD cohort. The PMA (P150030) was reviewed by the FDA and approved on October 17, 2016. A condition of the approval was that long term follow-up data to the 10-year postoperative interval for the enrolled DOD cohort subjects continue to be reported to the FDA. The original study protocol already included a requirement for subject follow-up to the 10-year postoperative interval, thus no protocol revision of the original study was required. The post-approval study protocol of the DOD cases described in this document describes the long-term follow up requirements included in the original study, and addresses the FDA's requirements for post-approval reporting of clinical study results. Subjects in this post-approval study have already signed informed consent forms agreeing to be followed to the 10-year postoperative interval. No additional consenting is required. Study data for these subjects up to, and including, 3-year follow-up results has already been reviewed in the PMA and is not part of this protocol. The follow- up requirements to the 10-year postoperative interval in the original study protocol have been reviewed and approved by the participating study sites' Ethic Committees (EC). No new subjects will be enrolled. Study data will continue to be collected on the original study's case report forms (CRF).

1.2. Study Rationale

This study is being conducted to comply with FDA requirements of post-market surveillance of the R3 delta Ceramic Acetabular System.

Document date : 01 Feb 2017; version 2.0 Confidential & Proprietary Page 7 of 25

Post-Approval Study of the R3 Biolox delta Ceramic Acetabular System – Europe	Protocol Number: R3H01/02/01/2017/Version2.0
	PMA Number P150030
	ADDENDUM Page: 8 of 25

2. STUDY OBJECTIVES

The primary objective of this phase of this study is to confirm that the safety and effectiveness of the R3 Biolox delta Ceramic Acetabular System (DOD) is maintained in the long term (to 10 years).

2.1. Primary Endpoint

The primary endpoint is implant survivorship at 10 years post study procedure.

The KM survivorship estimate for the DOD group in the PMA cohort at 3 years is 99.3% (95%CI: 97.4%-100.0a). Since this Post-Approval Study (PAS) is intended to document the long-term survivorship of the DOD treatment group only and no comparison to a control is required, no formal statistical hypothesis testing will be conducted.

2.2. Secondary Endpoints

Secondary endpoints include the following:

- Patient outcomes as measured using the modified Harris Hip Score;
- Radiographic evaluation to assess radiographic success defined as:
 - No radiolucencies greater than 2 mm in 50% or more in any of the cup or stem zones; and
 - No femoral or acetabular subsidence greater than or equal to 5mm from baseline; and
 - No acetabular cup inclination changes greater than 4 degrees (4°)

Document date : 01 Feb 2017; version 2.0 Confidential & Proprietary Page 8 of 25

Post-Approval Study of the R3 Biolox delta Ceramic Acetabular System – Europe	Protocol Number: R3H01/02/01/2017/Version2.0
	PMA Number P150030
	ADDENDUM Page: 9 of 25

3. STUDY DESIGN

This is a prospective, multicenter, observational study that is currently in the follow-up data collection phase. Five of the seven study sites that contributed data to the PMA cohort will participate in this PAS. The two sites that willnot participate in the PAS did not enroll any R3 Biolox delta Ceramic Acetabular System (DOD) PMA subjects, as such their data is not suitable for this PAS. The DOD treatment arm of the PMA Cohort included 137 DOD subjects.

Of the 137 DOD subjects included in the PMA Cohort, one died and one was revised by the 3-year follow-up interval. A total of 135 subjects are therefore eligible for this PAS study and all attempts will be made to continue follow-up on all subjects through the 10-year postoperative interval. Telephone follow-up for determination of device survival or revision status, and patient satisfaction in cases where subjects fail to return for follow-up visits will be conducted.

Document date: 01 Feb 2017; version 2.0 Confidential & Proprietary Page 9 of 25

Post-Approval Study of the R3 Biolox delta Ceramic Acetabular System – Europe	Protocol Number: R3H01/02/01/2017/Version2.0
	PMA Number P150030
	ADDENDUM Page: 10 of 25

4. STUDY DEVICE

The R3 delta Ceramic Acetabular System is a ceramic-on-ceramic hip prosthesis composed of modular components that include an R3 porous coated acetabular shell, alumina ceramic acetabular shell liner, an alumina ceramic femoral head, and one of four titanium alloy femoral stems. This acetabular system is used in combination with one of four titanium alloy femoral stems to comprise a total hip replacement. All implantable devices are for single use.

5. STUDY POPULATION

5.1. Subject Enrollment

All study sites and subjects have been recruited and enrollment is closed. DOD cohort subjects that were included in the PMA will continue to be followed as per the follow-up schedule established in the European Post-market Study until they reach the 10-year postoperative interval. Site agreements and signed patient informed consents are already in place and allow for the long-term data collection to 10 years proposed in this PAS.

5.2. Subject Inclusion Criteria

Subjects who met all inclusion criteria and none of the exclusion criteria for inclusion of their records in the PMA Cohort presented in the R3 Biolox Delta Ceramic Acetabular System PMA clinical report (subjects in the DOD treatment arm of the PMA Cohort) will be included in this PAS.

The inclusion criteria for the original European Post-market study are provided below for reference.

- Patient is 18-75 years old and he/she is skeletally mature
- Patient requires primary total hip arthroplasty due to non-inflammatory degenerative joint disease (e.g. osteoarthritis, post-traumatic arthritis, avascular necrosis, dysplasia/ developmental dysplasia of the hip) or inflammatory joint disease (e.g., rheumatoid arthritis)
- Patient has met an acceptable preoperative medical clearance and is free from or treated for cardiac, pulmonary, hematological, etc., conditions that would pose excessive operative risk
- The patient is willing to comply the follow-up schedule

All subjects included in the PMA cohort were required to have signed study informed consent forms, and have device labels confirming the implants used for surgery.

5.3. Subject Exclusion Criteria

Subjects in any of the other treatment arms of the original European Post-market Study are excluded from this PAS.

Document date : 01 Feb 2017; version 2.0 Confidential & Proprietary Page 10 of 25

Post-Approval Study of the R3 Biolox delta Ceramic Acetabular System – Europe	Protocol Number: R3H01/02/01/2017/Version2.0
	PMA Number P150030
	ADDENDUM Page: 11 of 25

The exclusion criteria for the original European Post-market study are provided below for reference.

- Patient has active infection or sepsis (treated or untreated)
- Patient is a prisoner or has an emotional or neurological condition that would pre-empt their ability
 or unwillingness to participate in the study including mental illness, mental retardation, linguistic
 insufficiencies (i.e. immigrants), or drug/alcohol abuse,
- Patients with acute hip trauma (femoral neck fracture)

Additional exclusion criteria for DOD subjects in the PMA cohort:

• Any subject in the DOD arm who was implanted with any hip system component (other than the ceramic acetabular liner) that is not US FDA 510(k) cleared for use with the study ceramic head.

Document date: 01 Feb 2017; version 2.0 Confidential & Proprietary Page 11 of 25

Post-Approval Study of the R3 Biolox delta Ceramic Acetabular System – Europe	Protocol Number: R3H01/02/01/2017/Version2.0
	PMA Number P150030
2000	ADDENDUM Page: 12 of 25

6. STUDY PROCEDURES

6.1. Study Schematic

The PAS follow-up intervals and schedule of evaluations are provided in Table 1. Data to the 3-year postoperative interval was included in the PMA and is indicated as already collected. Since subjects have already consented to participation to the 10-year interval, data collection is in process and on-going.

Table 1.

Table 1.									
Study Activity	Preop	Intra	D/C	3M	1Y	3Y	5Y	7Y	10Y
		-					(± 6 Mo)	(± 6 Mo)	(± 6
Inclusion/exclusion	Already collected								
Informed consent	Already collected								
Demographics	Already collected								
Modified Harris Hip Score (mHHS)	Already collected					х	х	х	
Radiographic Eval	Already collected					Х	Х	Х	
Adverse Events	Already collected					Х	Х	Х	

6.2. Postoperative 5-, -7, and 10-Year Visits

At the 5-year, 7-year and 10-year postoperative visits subjects will be evaluated using the modified Harris Hip Score (mHHS). The mHHS includes a modification to the "Distance Walked" section of the Harris Hip Score to replace the number of blocks with actual distances since the term "blocks" is not commonly used as a measurement of distance in Europe.

AP and lateral radiographs will be taken at the 5-year, 7-year and 10-year postoperative visits. Radiographs will be evaluated by an independent evaluator according to a Smith & Nephew R3 Acetabular Hip Study Image Evaluation Protocol included in Appendix I.

An adverse event assessment will be conducted at each follow-up interval. Data from each visit will be recorded on the study CRFs (Appendix II).

Document date : 01 Feb 2017; version 2.0 Confidential & Proprietary Page 12 of 25

Post-Approval Study of the R3 Biolox delta Ceramic Acetabular System – Europe	Protocol Number: R3H01/02/01/2017/Version2.0				
	PMA Number P150030 ADDENDUM Page: 13 of 25				
111111111111111111111111111111111111111					

6.3. Telephone Follow-Up

If subjects are unable to return for follow-up visits to the investigator's office, they may be contacted by telephone to assess their status. Subjects will be asked whether the study device is in place or has been revised, and patient satisfaction will be assessed. This information will be recorded on the corresponding CRF.

Document date : 01 Feb 2017; version 2.0 Confidential & Proprietary Page 13 of 25

Post-Approval Study of the R3 Biolox delta Ceramic Acetabular System – Europe	Protocol Number: R3H01/02/01/2017/Version2.0				
	PMA Number P150030				
	ADDENDUM Page: 14 of 25				

7. SUBJECT COMPLETION AND DISPOSITION

7.1. Enrolled Subject

All subjects have been enrolled and signed an EC approved study informed consent that described follow-up to the 10-year postoperative interval. No additional enrollment will occur.

7.2. Conditions for Study Termination

All reasonable efforts should be made to retain the subjects for the 10-year duration of this study. If the subject has a revision of any component, the subject will be terminated from the study.

A. Voluntary Withdrawal

Study participation is voluntary and subjects may withdraw at any point during the study without giving their reason for doing so. A study termination form will be completed for all subjects who do not finish the study, to document the reason for the withdrawal in the CRF.

B. Lost to Follow-Up

Some actively enrolled subjects will not return for follow-up exams due to a variety of reasons. Study personnel will make a reasonable effort to contact the subject and document the following contact attempts prior to declaring a subject to be lost to follow-up: the subject has been contacted according to the study sites policies, but no less than 2 documented phone contacts and 1 certified letter without response. Copies of all attempts to reach the subjects per regular mail or email and/or the attempts to contact the subject via other means should be documented and such documentation should be kept with the subjects CRF. A subject will be considered lost to follow-up if he/she does not appear for the scheduled study visit for 2 consecutive visits and study personnel are unable to contact the subject.

C. Study Termination by Investigator/Sponsor

The Investigator may withdraw subjects from the study for many reasons, including but not limited to the following:

- subject noncompliance to study schematic
- subject lost to follow-up

The Investigator **should** withdraw subjects from the study:

- in case any component of the original hardware is revised/exchanged
- if the Investigator or the Sponsor stops the study for any reason

For each case, information will be obtained on the Study Termination Form, detailing circumstances leading to the withdrawal.

D. Study Site Discontinuation

Document date : 01 Feb 2017; version 2.0 Confidential & Proprietary Page 14 of 25

Post-Approval Study of the R3 Biolox delta Ceramic Acetabular System – Europe	Protocol Number: R3H01/02/01/2017/Version2.0			
	PMA Number P150030			
	ADDENDUM Page: 15 of 25			

A specific study site in this multicenter study may also warrant termination under the following conditions:

- non-compliance to Good Clinical Practice (GCP) or protocol
- major protocol deviations
- inaccurate or incomplete data
- unsafe or unethical practices
- safety or performance considerations
- investigator involuntarily discontinues participation in study

Document date : 01 Feb 2017; version 2.0 Confidential & Proprietary Page 15 of 25

Post-Approval Study of the R3 Biolox delta Ceramic Acetabular System – Europe	Protocol Number: R3H01/02/01/2017/Version2.0	
	PMA Number P150030	
	ADDENDUM Page: 16 of 25	

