5.5. Subject Withdrawal / Termination Criteria

Whilst subjects are free to withdraw from the study at any time. All reasonable efforts should be made to retain the subjects for the 10-year duration of this study.

Study Site Discontinuation

A specific study site in this multicenter study may also warrant termination under the following conditions:

- non-compliance to Good Clinical Practice (GCP) or protocol
- major protocol deviations
- inaccurate or incomplete data
- unsafe or unethical practices
- safety or performance considerations
- investigator involuntarily discontinues participation in study

Documentation of withdrawn and lost to follow-up patients

Some actively enrolled subjects will not return for follow-up exams due to a variety of reasons. Study personnel will make all reasonable efforts to contact the subject and document the following contact attempts prior to declaring a subject to be lost to follow-up: the subject has been contacted according to the study sites policies, but no less than 2 documented phone contacts attempts and 1 letter without response. Copies of all attempts to reach the subjects per regular mail or email and/or the attempts to contact the subject via other means should be documented and kept with the subjects Case Report Form (CRF). A subject will be considered lost to follow-up if he/she does not appear for the scheduled study visit for 2 consecutive visits and study personnel are unable to contact the subject. For all cases (withdrawn and lost to follow-up), information will be obtained on the Study Termination Form, detailing circumstances leading to the withdrawal.

Sites will be requested to contact non-respondent patients using phone calls, regular mail, e-mail, certified letters or other means to urge patients to return to a clinic for follow-up or ascertain if a patient has moved.

6. Medical Devices

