8. SAFETY REPORTING

All adverse events, regardless of their relationship to the study device, occurring from the time of study device implantation through to study completion should be recorded on the appropriate CRFs and reported as below.

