9. STATISTICAL PROCEDURES

9.1. General considerations

General summary statistics for numeric data will include the available records (n), the mean, the standard deviation (SD), the median, the minimum, and the maximum value. For categorical data, the count and percent of data will be presented with the percent based on the number of subjects with data. Implant survivorship will be measured from time of surgery to time of the first instance of removal of any device component for any reason. Subjects who do not experience a removal for any reason will be censored at the date of last data collection. Kaplan-Meier (KM) estimates will be provided by time point (life tables) and graphically (survival curves).

The Statistic Analysis Plan is found in Appendix III.

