4.4 Handling of missing and incomplete data

The number of patients with missing data will be presented under the "Missing" category, if present.

When continuous data are being summarized, only the non-missing values will be evaluated for computing summary statistics.

A sensitivity analysis will be carried out comparing results of the original analysis to the results of an analysis where all missing data are assumed to be failures.

A second sensitivity analysis will be carried out using multiple imputation of the missing data in the form of a tipping point analysis. Multiple scenarios will be analyzed, each with a different number of missing data points imputed as successes for each treatment group. (Missing data points not imputed as successes will be imputed as failures.) The purpose of the analysis is to find the tipping point where a certain number of success imputations for each treatment group causes the inference to reverse.

In general, partial dates will be imputed as follows:

- if only the day is missing, the first day of the month will be assumed;
- if the day and the month are missing, January 1st will be assumed;
- if a date is completely missing or unknown the patient's data will not be included for analysis

Protocol Number: TBD Version 0.3

Forms							
Title	Title Statistical Analysis Plan Template						
Co	Code Version Effective Date Page						
FRM_S	FRM_ST03_032 0.3 23 Apr 2015 9 of 12						

5. Evaluation of Demographic and Baseline Characteristics

Given the nature of this study, the demographic data have been already obtained. The demographic and baseline characteristics will be summarized using descriptive statistics for the Enrolled Set.

6. Patient Accounting

Patient accounting will be presented according to the recommendations in the FDA guidance entitled "Clinical Data Presentations for Orthopedic Device Applications".

- Actual A: Subjects with complete data for the primary endpoint, evaluated per protocol, in the window time frame.
- Actual B: Subjects with any follow-up data reviewed or evaluated by investigator ("all evaluated" accounting).
- Theoretical: Number of subjects that would have reached the beginning of the study window associated with each visit if all subjects returned.
- Deaths: Cumulative number of subjects that died during or prior to the study visit.
- Failures: Cumulative number of subjects that failed (revision) during or prior to the study visit.

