7.2 Analysis of secondary efficacy endpoints

Secondary endpoints include the following:

- Patient outcomes as measured using the modified Harris Hip Score;
- Radiographic evaluation to assess radiographic success defined as:
 - -No radiolucencies greater than 2 mm in 50% or more in any of the cup or stem zones; and
 - -No femoral or acetabular subsidence greater than or equal to 5mm from baseline; and
 - -No acetabular cup inclination changes greater than 4 degrees (4°) and

These endpoints will be summarized using descriptive statistics and presented for all post-operative visits.

8. Evaluation of Safety

The number of AEs, SAEs, USADEs, Reoperation and Revisions, and the number and the percentage of patients experiencing AEs, SAEs, USADEs will be presented for the enrolled set.

The number of AEs and the number and the percentage of patients with at least one AE will be presented for AEs, and SAEs.

The number and the percentage of patients with at least one AE will be presented by severity, seriousness, device relatedness and procedure relatedness.

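### In the post-approval study, subjects leave at first revision, so later radiographic-success and mHHS results describe unrevised hips only and events after a revision may go uncollected

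*Combined protocol and SAP*

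**What the plan says.** **Termination.** Addendum 7.2 says "If the subject has a revision of any component, the subject will be terminated from the study". Its part C repeats the rule, listing among the cases where the investigator should withdraw a subject "in case any component of the original hardware is revised/exchanged".

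**Main protocol.** Section 5.5 says "All reasonable efforts should be made to retain the subjects for the 10-year duration of this study" and contains no termination at revision. The same sentence opens Addendum 7.2, where the termination rule follows it directly. Main protocol 4.2 asks for all adverse events in study patients up to ten years. Addendum 8 covers events "occurring from the time of study device implantation through to study completion should be recorded".

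**Summaries.** Addendum 9.1 presents categorical data "with the percent based on the number of subjects with data". SAP 4.4 says that for continuous data "only the non-missing values will be evaluated for computing summary statistics". On mHHS and radiographic success, SAP 7.2 says "These endpoints will be summarized using descriptive statistics and presented for all post-operative visits", and gives no rule for subjects already revised.

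**Sensitivity analyses and accounting.** SAP 4.4 plans one analysis with all missing data taken as failures and one tipping-point analysis. SAP 6 reports cumulative revisions as failures, and subtracts deaths and revisions to obtain the number expected at each visit.

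**The concern.** Taken together, these provisions remove subjects because of their outcome. A subject whose head, liner, stem or shell is exchanged has no later mHHS or radiograph and drops out of the denominator at every later visit. The subjects removed are the known device failures. The radiographic-success percentage is therefore higher than it would be if they were kept as failures, and the mean mHHS is higher if revised patients score worse. Nothing in SAP 7.2 tells the reader that the result is restricted to unrevised hips.

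The second issue is data collection. After exchange of a head, for example, the R3 shell may still be in place, and the Addendum's objective is to confirm safety and effectiveness to 10 years. Once the subject is terminated, it is unclear whether later adverse events, reoperations or re-revisions are still recorded. SAP 9 lists failure to withdraw a subject as required by the protocol as a deviation. A site that keeps following a revised subject, as main protocol 5.5 permits, could therefore be recorded as deviating.

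**Working it through.** **Inputs from the documents.** The PMA cohort has 137 DOD subjects, with one death and one revision by 3 years (Addendum 3 and 9.2). The 3-year Kaplan-Meier estimate is 99.3% (SAP 3.5.1). The main protocol hypothesis for the R3 cup is at least 90% survivorship at 10 years (main protocol 3).

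**Reproducing the plan's figures.** Eligible for the PAS: 137 − 1 − 1 = 135, as stated. One event in 137 gives 1 − 1/137 = 99.27%, which rounds to the stated 99.3%.

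**Assumptions not in the documents.** Radiographic success in unrevised hips is p = 95%. Every unrevised subject is evaluable, so deaths and loss to follow-up are ignored. The number of revisions r is 1 (known by 3 years), 7 (about 95% survivorship) or 14 (about 90%). N = 137, so that the subject already revised is included.

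**Radiographic success.** The available-case result is p. With revised subjects kept as failures it is p × (N − r)/N, so the overstatement is p × r/N.

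| Revisions r | Available-case | Revised counted as failures | Overstatement |
|---|---|---|---|
| 1 | 95.0% | 0.95 × 136/137 = 94.3% | 0.7 points |
| 7 | 95.0% | 0.95 × 130/137 = 90.1% | 4.9 points |
| 14 | 95.0% | 0.95 × 123/137 = 85.3% | 9.7 points |

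Varying p from 85% to 100% gives 0.6 to 0.7 points at 1 revision and 8.7 to 10.2 points at 14.

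**mHHS.** The shift in the mean is (r/N) × d, where d is the assumed deficit in revised subjects. For d = 10 to 30 points it is 0.07 to 0.22 points at 1 revision and 1.0 to 3.1 points at 14.

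**Does SAP 4.4 repair this?** With 14 revisions and no other missing data, the missing-equals-failure analysis gives 85.3% if revised subjects count as missing. It stays at 95.0% if they do not count because SAP 6 no longer expects them. Now suppose 10% of the 123 unrevised subjects are also lost. Then 110.7 are evaluable, of whom 0.95 × 110.7 = 105.2 are successes:

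- revised subjects alone as failures: 105.2/(110.7 + 14) = 84.3%;
- all missing as failures, revised included: 105.2/137 = 76.8%;
- all missing as failures, revised excluded: 105.2/123 = 85.5%.

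The SAP does not say which of the last two is meant, and neither separates known failures from loss to follow-up. The tipping-point analysis is worded for treatment groups and an inference that could reverse, whereas the PAS has one group and no hypothesis test. mHHS has no failure definition, so neither analysis applies to it directly.

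**The case against.** The strongest reply is that revisions are not hidden. The primary Kaplan-Meier analysis counts first removal of any component as the event (SAP 7.1). Patient accounting shows cumulative revisions by visit (SAP 6). A reader can therefore set the revision count beside each secondary result. This stands, and it limits the point to the descriptive secondary endpoints.

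A reader might also infer that the safety tables become too favourable. The documents do not support that. SAP 8 reports adverse event percentages for the enrolled set, not for subjects with data, and each revision is documented as an adverse event. Termination does not lower the share of patients with at least one event. Only events after the first revision are at risk of being lost.

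A reader might further infer that DOD subjects are certainly followed differently from other bearings, or that the rule breaches the main protocol's ITT principle. Neither is shown. Addendum 1.1 and 5.1 say follow-up continues as in the original study, so it is ambiguous whether termination refers to the PAS alone. Main protocol 5.3 explains ITT through patients who consented but did not receive the planned treatment; it does not address follow-up after revision.

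Finally, radiographic change is measured against the discharge film, and a replaced component has no such baseline. A revision for infection is also not a radiographic failure as SAP 3.5.2 defines it. Reporting unrevised hips is therefore a legitimate descriptive choice, and carrying the last mHHS before revision forward would bring its own bias. This argues for a label and a companion row, not for a new definition of the endpoint.

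**Conclusion.** The point holds for the secondary endpoints and for data after a revision. As written, later radiographic-success and mHHS results exclude known failures without saying so, and SAP 4.4 does not clearly correct this.

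The size depends on the number of revisions by 10 years, which is unknown. At the only count the documents give, the overstatement of radiographic success is about 0.7 points. Values of 4.9 and 9.7 points need 7 and 14 revisions, and the 14 corresponds to the main study's minimum hypothesis across bearings, not to an expectation for this cohort. All three figures assume 95% success in unrevised hips and no other missing data. The mHHS shift rests on an assumed deficit and is about 3 points at most in the range examined.

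The primary endpoint is unaffected, and with no hypothesis test planned, no formal conclusion would reverse. The change is worth making because it is cheap and the direction of the effect on radiographic success is known.

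**What to change.** 1. In SAP 7.2, label the available-case radiographic and mHHS results as unrevised hips. Add a prespecified companion row for radiographic success that keeps every previously revised subject, including the one revised by 3 years, in the denominator as a failure.
2. In SAP 4.4, state that revised subjects count as failures in the missing-equals-failure analysis, and show them separately from loss to follow-up.
3. Reconcile Addendum 7.2 with main protocol 4.2 and 5.5 and with Addendum 8, so that adverse events, further removals and vital status are still recorded to 10 years after a revision. The consent to 10-year follow-up is already signed (Addendum 1.1 and 7.1). The adverse event and telephone forms already have fields for component removal, and the adverse event form has fields for death.

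The cost is some SAP and Addendum wording, one extra table row, continued collection for a few subjects, and a somewhat less favourable secondary figure.
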